3. ENROLMENT

A total of 90 subjects will be recruited by the facilities involved in this Clinical Study. Both hospitalised patients and outpatients receiving treatment will be considered for inclusion in this Study.

Patients will be assessed using a standard procedure that includes taking a medical history and a physical examination.

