3.1 Inclusion criteria

- Subjects with venous, arterial or mixed skin ulcers and surgical wound dehiscence (18), (19);
- Presence of multiple similar wounds or one wound measuring² at least 5 cm;
- Men and women ≥ 18 years of age;
- Patients must be able to understand the aims of the Clinical Study and provide their informed consent in writing;
- Chronicity of the wound: at least 8 weeks.

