3.2 Exclusion Criteria

The following will not be included in this study:

- Patients who participated in a clinical study on skin ulcer healing during the previous month;
- Patients who are unable to understand the aims and the objectives of the study;
- Patients with neoplastic ulcers;
- Patients with decubitus ulcers;
- Patients with diabetic foot ulcers;
- Patients with clearly infected ulcers;
- Patients with ulcers caused by critical ischaemia;
- Patients with a history of self-harm that can purposely alter the healing process;
- Patients with psychiatric disorders;
- Pregnant or breastfeeding women³;
- Patients with neoplasms or other diseases involving the use of cytostatic or immunosuppressive drugs;
- Patients with a short life expectancy.

In order for subjects to be eligible for inclusion in the treatment phase, all inclusion and exclusion criteria must be met before enrolment. Any concomitant drug therapies must be maintained.

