For each new patient, the Principal Investigator or his/her delegate will complete the Patient Enrolment Form with information such as patient identification (Name and Surname will be the same as in the Case Report Form, i.e., site ID code and number), age, gender, root cause of the ulcer, any concomitant conditions, any pharmacological therapies, date of onset of ulcers and recruitment date.

The second part of the form contains a table for recording the visit date, the patients' general health and the data collected at each visit.

Recording of clinical data

The data pertaining to the evaluation of the study endpoints will be acquired at specific time points as indicated in the Protocol and in the Study Case Report Form.

The parameters recorded on the Case Report Form will be acquired and maintained in paper format for the entire duration of the trial and stored both in paper and digital format, after scanning the Case Report Form, once a patient has completed the study; photographic images of wounds will be acquired, maintained and stored in digital format for the entire duration of the trial and afterwards.

The archiving code follows the patient recruitment code and the time of acquisition.

Case Report Form

The same Case Report Form will be used for all patients. It consists of many columns to be completed, one for each observation time point. At each observation time point, the doctor will mark the value chosen for each parameter with an "X" and the most appropriate description.

The Case Report Form will include a "Notes" section for recording additional information not initially envisaged that may be useful during the data analysis phase (e.g., patient's ethnic origin, special environmental conditions, patient's specific health conditions such as influenza or others, etc.).

Following the patient's completion of or withdrawal from the study, the Case Report Form will be scanned and archived.

Centralised database

The Principal Investigator of each site will send the Enrolment Form of any new recruited patients as well as the photographic records of the follow-up patients to the Project Manager on a weekly basis. The Case Report Forms of all patients who leave the study, whether healed or identified as drop-outs, will also be submitted.

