If, at recruitment, a patient has more than one wound with a **diameter greater than 5 cm**, all wounds will be divided into two halves along the longest side and treated as described above.

After treatment with the EmoLED device, the wound will be dressed with a hydrofibre dressing. If clinical signs of infection occur, the wound will be dressed with a hydrofibre dressing with silver. The limb will then be bandaged with a compression bandage.

4.1.2 Standard treatment and data recording.

Any wounds or parts of wounds that are not treated with the EmoLED device will be medicated using the standard treatment consisting of a hydrofibre dressing or hydrofibre dressing with silver (as described above) and compression therapy. Ultimately, the treatment differs only for the fact that the EmoLED device is used in accordance with the procedure described above, while the rest of the treatment remains unchanged.

Following enrolment and the signing of the Informed Consent Form, the pertinent data from each patient will be recorded in the respective Case Report Form according to the following schedule: W0 (Week 0: enrolment and first treatment), W1, W2, W3 ... to W10, as per the routine visits over the 10-week period from enrolment.

Patients may miss a maximum of two non-consecutive follow-up visits over the 10-week period, starting from visit 5. Patients will be excluded from the study if consecutive visits are missed.

The parameters used to define the study outcomes will be based on:

- photographic images of the wounds treated with the EmoLED device as well as of control wounds
- Case Report Form completed by the doctor during the visits.

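### Arterial and mixed ulcers are eligible unless caused by critical ischaemia, yet Sections 4.1.1 and 4.1.2 prescribe compression with no condition on arterial supply

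*Combined protocol and SAP*

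**What the plan says.** Section 3.1 admits "Subjects with venous, arterial or mixed skin ulcers and surgical wound dehiscence". Section 3.2 removes "Patients with ulcers caused by critical ischaemia". No other exclusion is framed in terms of arterial supply, and neither section sets a perfusion threshold.

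Section 4.1.1 closes its account of care after the device session with "The limb will then be bandaged with a compression bandage". The sentence just before it does carry a condition: "If clinical signs of infection occur, the wound will be dressed with a hydrofibre dressing with silver".

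For the control side, Section 4.1.2 defines standard treatment for every wound or wound part left without the device. The components it names end with "hydrofibre dressing with silver (as described above) and compression therapy"; a plain hydrofibre dressing is the alternative to the silver one. It adds that use of the device is the only difference between the two areas.

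The information needed to judge arterial supply is partly in hand. Under Section 3, "Patients will be assessed using a standard procedure that includes taking a medical history and a physical examination". The enrolment form in Section 3.3 captures "root cause of the ulcer, any concomitant conditions, any pharmacological therapies". Section 5 has signs looked for at each study visit. Nothing links any of this to the decision to compress, and no bandage type or pressure is specified.

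**The concern.** The eligibility rule and the background-care rule do not fit together. Compressing a limb whose arterial supply is already reduced may reduce perfusion further. That statement rests on general clinical principle; the documents do not discuss it. The plan deliberately enrols patients to whom the principle applies and then prescribes compression without asking about their arterial supply.

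Two things are at stake. The first is the safety of patients with non-critical arterial or mixed disease. The second is the position of the investigator: one who sensibly withholds compression has no written permission to do so. In a multicentre study, sites may resolve that differently. The trial's inference is not at stake.

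**Working it through.** The point is one of reading, so the relevant provisions are set side by side. The sample-size check at the end only confirms that nothing there depends on compression.

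**1. Who can enter.** Section 3.1 names 4 wound groups: venous, arterial, mixed and surgical dehiscence. Two of the 4 are arterial or mixed. Section 3.2 lists 12 exclusions, of which 1 (critical ischaemia) is framed in terms of arterial supply. Arterial and mixed ulcers not caused by critical ischaemia therefore stay eligible.

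**2. What they receive.**

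| Instruction | Section | Condition attached |
|---|---|---|
| Hydrofibre dressing after the device | 4.1.1 | none |
| Silver dressing | 4.1.1 | clinical signs of infection |
| Compression bandage on the limb | 4.1.1 | none |
| Compression as part of standard treatment | 4.1.2 | none |

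There are 2 compression statements, and 0 depend on aetiology or perfusion. One covers the device area and the other the control area. Section 6 places each subject in both groups, so both statements bear on every patient with limb wounds. The silver-dressing sentence shows that the authors wrote a condition where they intended one.

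**3. Whether other text supplies the condition.**
- Section 1 describes the device as an adjuvant to standard therapy, and Section 4.1 as an addition to the patient's own standard therapy. Both are general; 4.1.2 then defines standard treatment and includes compression.
- Section 2 lets patients continue their usual topical therapy. That does not make compression conditional.
- Section 8 refers to Standard Operating Procedures and other written instructions, which are not in the documents. It also makes the Coordinator responsible for protocol compliance.

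None of these makes compression depend on arterial supply.

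**4. What is and is not allowed.** With no pressure or bandage type fixed, reduced compression complies with the text. Omitting compression does not.

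**5. Exposure of an affected patient.** Visits run from W0 to W10: 10 + 1 = 11 scheduled visits over 10 weeks, fewer if the wound heals earlier. The number of such patients cannot be computed, because no expected mix of aetiologies is given.

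**6. Inference.** Compression is meant to be the same in both areas of a patient, so the rule does not favour either side of the pair.

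The sample size in Section 6 uses an SD of 50, a difference of 20, one-sided α = 0.05 and power 80%. SD of the difference = 50·√(2(1 − ρ)), and d = 20 / SD of the difference. The result is the smallest n at which a paired t-test with effective size 0.864·n reaches 80% power. The factor 0.864 is the standard minimum asymptotic relative efficiency; it is assumed, since the plan names the method without giving the number.

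| ρ | SD of difference | d | n recomputed | n in plan |
|---|---|---|---|---|
| 0.1 | 67.08 | 0.298 | 83 | 83 |
| 0.3 | 59.16 | 0.338 | 65 | 65 |
| 0.5 | 50.00 | 0.400 | 47 | 47 |
| 0.7 | 38.73 | 0.516 | 29 | 29 |

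The plan's figures reproduce exactly. No input relates to compression, so the calculated 83 and the planned 90 stand.

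**The case against.** The best reply is that compression is described here as ordinary background care, which clinicians apply with judgement. The severe arterial cases are excluded, patients are examined at enrolment and seen weekly, and the open pressure level lets an investigator adapt the bandage. The documents record no compression-related harm, and site procedures that cannot be seen may already cover contraindications.

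Much of this stands, and it is why the flaw is modest. It does not remove the flaw. The exclusion governs who enters, not how an admitted arterial patient is bandaged, and examining a patient has no written consequence for compression. Section 4.1.2 states what standard treatment consists of, and Section 8 requires that the protocol be followed.

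A second objection is that conditional wording could let a patient's two areas receive different compression, which the present text avoids. That is correct, and the fix has to guard against it.

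Stronger readings are tempting but unsupported:
- **A dehiscence away from a limb must be compressed.** A reader might infer this because 3.1 names no body site and 4.1.2 covers any untreated wound. That argues from silence. Section 4.1.1 speaks of the limb, and the sample-size assumptions in Section 6 draw on leg-ulcer literature. An off-limb wound simply would not be bandaged, and no harm follows. This is a wording gap only.
- **Full compression is mandatory whatever the arterial supply.** No pressure is set, so reduced compression is already open.
- **The treatment comparison is biased or underpowered.** Background care is intended to be equal within each patient, and the sample size does not involve compression.

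**Conclusion.** The point holds as a modest patient-safety flaw in a stated rule, and it should be fixed. Limbs with non-critical arterial disease are compressed if the text is followed, and omitting compression is a departure from protocol. For an affected patient this can recur at up to 11 visits; how many patients are affected is unknown. There is no effect on bias or sample size.

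The conclusion rests on three assumptions: that the clinical principle about compression and reduced arterial supply applies to these patients; that 4.1.1 and 4.1.2 are read as instructions, not as loose descriptions of usual care; and that no unseen site procedure already supplies the missing condition.

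**What to change.** In both 4.1.1 and 4.1.2, replace the unconditional wording with a clause to this effect: compression is applied to limb wounds only where the investigator judges, from the enrolment history, the physical examination and the ulcer aetiology, that arterial supply permits it; otherwise reduced or no compression is used.

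Add that the treated and control areas of a patient receive the same compression. Where two wounds lie on different limbs and cannot safely be given the same compression, record this on the CRF so that the pair can be identified. The halves of a split wound share a site and normally one bandage, so the exception should not arise for them.

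The cost is one clause in two places and a CRF entry. Section 3.3 already provides a CRF column for each observation time point and a notes section; the form itself is not in the documents, so compression may already be recorded. No new test, visit, eligibility change or sample-size recalculation is needed. The downside is slightly more varied background care between patients.

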4.2 Primary endpoint of the study

The primary endpoint of the study will be a comparison of the outcomes in terms of percentage reduction of the area of the wound treated with the EmoLED device versus the wound treated with SOC at W10, both the difference in the individual patient and within the entire group of 90 recruited patients.

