6. STATISTICAL PLAN

Ninety subjects will be enrolled in this study. Each subject is part of both the control group and the treatment group.

Given that each patient will both receive the treatment and will also be a control subject, both groups will contain the same number of subjects, even if some of the subjects withdraw from the study. A comparative study of the subjects' demographic data and other baseline characteristics will also not be necessary as the two groups will be perfectly superimposable.

Treatment will be administered immediately after the cleaning and any necessary debridement of the complete wound. The area of the wound that should not be treated with the EmoLED device will be duly marked and covered with different layers of sterile dressing; this facilitates treatment standardisation and uniformity, thereby limiting any variability; it will also enable the treated, untreated and adjacent areas of each subject to be coherently defined.

The aim of the statistical analysis will be to establish the efficacy of the treatment with the EmoLED device; the significance ($p<0.05$) of any difference observed in the healing process between treated and untreated areas will be evaluated. Specifically, the primary endpoint of the study is the percentage reduction of the area of the wound treated with the EmoLED device versus the wound not treated with the EmoLED device at W10.

The secondary endpoints are:

1. Treatment safety.
2. Outcomes comparison in terms of the percentage reduction of the area of the wound treated with the EmoLED device versus the wound treated with SOC only within the ten-week observational period.
3. Evaluation of difference in healing time between the two areas.
4. Pain reduction (with pre-treatment assessment on a 0-10 VAS)
5. (OPTIONAL) Depending on the patient's willingness to continue to go to the study site, the observation of any unhealed area(s) over the 10-week period can be extended until complete healing or up to 20 weeks.

Estimation of sample size

The considerations underlying the choice of the model described below were drawn from a review of the literature on leg ulcer therapies and healing dynamics as well as on past clinical experience data obtained by the sites involved in the study with the treatment in question.

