The most significant finding yielded by the analysis of the clinical data in our possession is an expected 30% variability in the percentage reduction of the area of the wound at week 10. This value was confirmed by [15], where it was used to estimate the sample size. On the other hand, [16] found the standard deviation of the percentage reduction of the area of the wound to be 53% in the worst case and limited to venous ulcers only.

The analysis for the calculation of the sample size is based on:

- the clinical objective, which is represented by the percentage reduction of the area of the wound at W10
- a non-parametric statistical instrument for paired data, namely the Wilcoxon signed-rank test
- an a priori hypothesis of expected variability of 50% (conservative value)
- an expected 20% mean difference in the percentage reduction between the treated and the non-treated area
- a statistical power of 80% ($\beta=0.2$) and $\alpha=0.05$ will be considered
- a unilateral alternative hypothesis: the EmoLED treatment does not result in worsened outcome
- A correlation coefficient between percentage reductions of the treated and untreated area of 0.1, 0.3, 0.5 and 0.7
- A method for estimating the sample size based on asymptotic relative efficiency, compared to the t-test (minARE)

| | Estimate 1 | Estimate 2 | Estimate 3 | Estimate 4 |
|---|------------|------------|------------|------------|
| β | 0.2 | 0.2 | 0.2 | 0.2 |
| α | 0.05 | 0.05 | 0.05 | 0.05 |
| Diff. in % wound area reduction after 70 days | 20% | 20% | 20% | 20% |
| ρ | 0.1 | 0.3 | 0.5 | 0.7 |
| n | 83 | 65 | 47 | 29 |

The higher estimate is that relating to case 1, whose sample size is 83 subjects, which served as the basis for the choice of the number of subjects to be recruited, taking into account possible loss of subjects during treatment.

Statistical analysis of the primary endpoint.

A Wilcoxon signed-rank test with a significance level of 0.05 will be performed to evaluate the efficacy of use of the device. This test allows paired data to be handled and is robust enough to evaluate variability in observation distribution. A population analysis, as well as a per-protocol analysis (PP), will be performed for the subjects who complete the study.

Statistical analysis of secondary endpoints.

1. Treatment safety.

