Adverse event reports will be collected, analysed and managed according to the criteria indicated in 5.2. The most appropriate statistical instrument will be chosen for analysis based on the number and type of adverse events reported.

2. Outcomes comparison as percentage reduction of the area of the wound treated with the EmoLED device versus the wound treated with SOC alone during the 10-week observation period.

Both the areas of the wound treated with the EmoLED device and those not treated with the EmoLED device, as measured on the required observation days, will be considered. A statistical analysis of paired data will be

performed using repeated measurements. In particular, both a comparison of the measurements obtained on different days, separately, and an analysis that will take into account the global trend over the observation period, will be performed.

Tests for data paired to pairs of measurements obtained on different observation days will be performed in the first case. These tests will be applied separately to the various days, evaluating any significant differences in both treated and untreated areas. The adopted statistical test will be either a parametric (t-test) or a non-parametric test (Wilcoxon signed-rank test) depending on the observed data distribution. The statistical significance will be corrected for multiple comparisons (e.g., given the possibility of a positive correlation between the identified measurements, Benjamini-Hochberg correction will be considered).

In the second case, the area under the curve (AUC) will be evaluated for each subject and in each area in order to obtain information on possible differences between changes in the treated and untreated areas of the wound. Either parametric or non-parametric paired data tests (depending on parameter distribution) will be performed in order to evaluate any differences in the trends of this parameter summarising the healing dynamics both in the treated and untreated areas.

The mean value observed in the remaining subjects will be used for both approaches if there is any missing data. A sensitivity analysis will be performed using both the best value and the worst value observed in the subjects.

3. Evaluation of the difference in healing time between the two areas.

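### The missed-visit allowance in 4.1.2 does not exempt W10, the follow-up visit that defines the primary endpoint, and no rule says how a missing W10 area enters the primary test

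*Combined protocol and SAP*

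**What the plan says.** Section 4.1.2 sets the visit schedule as "W0 (Week 0: enrolment and first treatment), W1, W2, W3 ... to W10, as per the routine visits over the 10-week period from enrolment". It then gives the allowance: "Patients may miss a maximum of two non-consecutive follow-up visits over the 10-week period, starting from visit 5". The only stated consequence concerns runs of absences: "Patients will be excluded from the study if consecutive visits are missed". No visit is exempted.

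Section 4.2 defines the primary endpoint as the "percentage reduction of the area of the wound treated with the EmoLED device versus the wound treated with SOC at W10", and refers it both to the individual patient and to the whole group of 90 recruited. Section 6 repeats the time point: "the percentage reduction of the area of the wound treated with the EmoLED device versus the wound not treated with the EmoLED device at W10".

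Section 6 tests this with a Wilcoxon signed-rank test, in a population and a per-protocol analysis of subjects who complete the study. It does not define completion. The sample size is 83, and 90 are recruited, "taking into account possible loss of subjects during treatment".

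The one missing-data rule stands under secondary endpoint 2: "The mean value observed in the remaining subjects will be used for both approaches if there is any missing data". The two approaches are the day-by-day paired tests and the AUC comparison. A best-value and worst-value sensitivity analysis follows it.

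Section 2 ends monitoring at healing if that comes before week 10, and at week 10 otherwise.

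**The concern.** The visit rule and the primary endpoint do not fit together. The rule tolerates absence at any visit from visit 5 to the end of the 10 weeks, while the primary comparison needs an area measurement at the last of them. An absence that the protocol permits can therefore remove a primary value, and nothing says whether that patient is then dropped, imputed, carried forward or measured late.

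Two things are at stake. The first is the number of pairs in the primary test, because permitted W10 absences and true dropouts share one small margin. The second is pre-specification: with no rule for the primary test, the handling could be chosen after the data are seen. If areas healed before W10 are scored as 100% reduction (natural, but not stated), the gap falls on patients with an area still open, so the missing values would not be a random subset of outcomes.

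**Working it through.** **1. Does W10 fall inside the allowance?** The text does not say whether visit 5 is W5, or W4 with W0 counted as the first visit. Both readings were enumerated, with at most two misses and no two adjacent.

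- Visit 5 = W5 (six visits, W5 to W10): 1 pattern with no miss + 6 with one miss + (15 − 5) = 10 with two, 17 in all. W10 is missed in 5: alone, or with W5, W6, W7 or W8.
- Visit 5 = W4 (seven visits): 1 + 7 + (21 − 6) = 23 patterns. W10 is missed in 6.

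So W10 may be missed on either reading. These are counts of what is allowed, not probabilities.

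**2. Reproducing the plan's sample size.** Inputs from section 6: SD of percentage reduction 50, mean difference 20, one-sided α = 0.05, power 80%, correlation ρ = 0.1, 0.3, 0.5 and 0.7, minARE method. The plan names minARE without its value; 0.864 was used.

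- SD of the paired difference = 50 × √(2(1 − ρ)); standardised effect d = 20 / SD of the difference.
- Effective n = 0.864 × n.
- Power = P(T > t₀.₉₅), where T is noncentral t with 0.864n − 1 degrees of freedom and noncentrality d × √(0.864n).

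For ρ = 0.1: SD of the difference = 50 × √1.8 = 67.08 and d = 0.298. At n = 83, effective n = 71.7, noncentrality = 0.298 × √71.7 = 2.52 and power = 80.4%. The smallest n reaching 80% is 83, 65, 47 and 29 for the four correlations, which matches all four figures in the plan.

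**3. Margin.** 90 − 83 = 7 patients, 7/90 = 7.8% of those recruited. No expected loss rate is stated.

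**4. Power by number of complete pairs (SD 50, one-sided).**

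| Pairs | ρ = 0.1 | ρ = 0.3 | ρ = 0.5 | ρ = 0.7 |
|---|---|---|---|---|
| 90 | 83.2% | 90.5% | 96.8% | 99.8% |
| 83 | 80.4% | 88.3% | 95.6% | 99.6% |
| 72 | 75.2% | 83.9% | 93.0% | 99.1% |

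**5. Assumed rates of W10 absence.** The documents give none, so a range is shown at ρ = 0.1, with missing pairs simply lost.

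| Missed W10 (assumed) | No other loss | With a further 10% dropout (assumed) |
|---|---|---|
| 5% | 86 pairs, 81.6% | 77 pairs, 77.7% |
| 10% | 81 pairs, 79.5% | 73 pairs, 75.7% |
| 20% | 72 pairs, 75.2% | 65 pairs, 71.3% |

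Pairs = 90 × (1 − dropout) × (1 − missed W10), rounded; for example 90 × 0.9 × 0.9 = 72.9, so 73.

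**The case against.** The strongest reply is that the literal reading of 4.1.2 is not the only one. Section 2 follows unhealed patients to week 10, section 3.3 has patients agree to return weekly, and section 6 analyses those who complete the study. A patient without W10 might be classed as a non-completer, which is the kind of loss that 90 against 83 is meant to absorb. This is a possible reading, but completion is undefined and 4.1.2 makes no exception for W10, so the documents do not settle it.

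It can also be said that a missing-data rule exists for this variable: the day-by-day tests of secondary endpoint 2 include W10, and mean imputation covers them. That stands as far as it goes. What is absent is a statement that the rule applies to the primary test. The optional observation up to 20 weeks foresees later measurements, but they are not named as a substitute for W10. The silence on a window means only that late measurement is unregulated, not that it is forbidden.

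Four stronger inferences are tempting and are not supported:

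- **That the pattern counts are absence rates.** Reading 5 of 17 as a probability assumes that every pattern is equally likely, and the documents give no attendance data.
- **That the primary result will be biased.** A missed visit removes both areas of a patient. General success or failure of healing does not by itself bias a within-patient difference; absence must be related to the difference between the areas. The documents do not show that it is.
- **That the trial becomes underpowered.** Step 4 shows power below 80% with 72 pairs only for ρ near 0.1. The plan calls its SD of 50 conservative and reports 30% as the expected variability.
- **That such absences would go unrecorded as deviations.** The documents contain no rule on recording deviations from which this could be read.

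Patients whose areas have all healed before W10 lose little by not attending, provided that 100% reduction is taken as their value.

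**Conclusion.** The point holds as a gap between the visit rule and the primary endpoint. Section 4.1.2 permits a patient with an open area to attend W9, skip W10 and remain within the rule, with no primary value and no stated way of handling its absence in the primary test.

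The likely size is modest and cannot be fixed from the documents. With no other loss, 7 missing W10 pairs use up the whole margin. In the planning case behind 83, 18 lost pairs (90 − 72) bring power from 83% to 75%; at ρ of 0.3 or more it stays at about 84% or above. These figures assume a one-sided test, SD 50, a true difference of 20 and pairs lost at random. Bias is possible, not demonstrated. This is a cheap improvement to make, not a flaw that undermines the design.

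**What to change.** In 4.1.2:

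- Limit the missed-visit allowance to visits before W10.
- Require the W10 photograph and area measurement of both areas for every patient still in follow-up with an unhealed area.
- If the day is missed, take the measurement at the next attendance within a stated short window (for example, plus or minus 1 week) and use it as the W10 value. Say which measurement counts if two fall within the window.

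In section 6:

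- Count an area healed before W10 as 100% reduction.
- State how a W10 value still missing after the window is handled in the primary Wilcoxon test, and define who counts as having completed the study.

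If patients with consecutive missed visits are also to be measured at W10, this must be reconciled with the exclusion sentence in 4.1.2.

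The cost is a few sentences in two sections, and some W10 measurements taken off the nominal day. The timing noise is slight and the same for both areas of a patient. Treatment, test and sample size do not change.
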